[figure not shown]

## 1. INTRODUCTION

### 1.1. Background and Rationale

Osteoporosis is characterized by a decrease in bone mass and architectural deterioration of bone tissue. Subtle modifications of bone remodeling, related to abnormalities of bone turnover, can induce a substantial loss of bone over a prolonged period of time. A period of asymptomatic bone loss results in reduced bone strength. When bone loss is sufficient to cause mechanical weakness, fractures may occur spontaneously or as a result of minimal trauma. Osteoporotic fractures cause substantial clinical and economic burden for society. Age and menopause are the two main determinants of osteoporosis. The cessation of ovarian production of estrogen, at the time of the menopause, results in an accelerated rate of bone loss in women.

Bazedoxifene (BZA) is a third generation non-steroidal selective estrogen receptor modulator (SERM) currently approved in the European Union (EU) for the treatment of postmenopausal osteoporosis in women at increased risk of fracture. BZA is an estrogen receptor ligand that exhibits tissue specific activity: BZA functions as an agonist in the bone and an antagonist in the breast and uterine endometrium. BZA was developed in tablet form and current dosing consists of once daily administration of a 20 mg tablet. BZA (Conbriza) was approved in Europe via the centralized authorization procedure in April 2009. The first EU launch occurred in Spain in September 2010 which will be followed by launch in Italy in April 2011.

Currently, one other SERM, raloxifene (Evista®) is marketed in Europe for the treatment and prevention of postmenopausal osteoporosis. Bisphosphonates are non-hormone compounds that bind to the bone surface and are then taken up by osteoclasts. Bisphosphonates have a profound effect on bone remodeling, and are widely used for the prevention and treatment of osteoporosis.

In clinical trials, BZA-treated women had an increased risk of venous thromboembolic events (VTEs) compared to placebo. VTEs are included in the product label as an important identified risk.

This observational cohort study is being conducted to further characterize selected adverse events of interest among a patient population prescribed bazedoxifene, raloxifene, or a bisphosphonate in usual clinical care outside of a randomized clinical trial setting. This post-authorization safety study (PASS) is a post-authorization commitment to the CHMP/EMA.

The product Summary of Product Characteristics (SmPC) will be used as the single reference safety document for expedited safety reporting purposes for this study.

## **2. STUDY OBJECTIVES AND ENDPOINTS**

### **2.1.1. Primary Objective**

To estimate and compare the incidence rates of venous thromboembolism (VTE) among women receiving bazedoxifene and women receiving a bisphosphonate for treatment of osteoporosis.

### **2.1.2. Secondary Objective**

To estimate and compare the incidence rates of VTE among women receiving bazedoxifene and women receiving raloxifene for treatment of osteoporosis.

To estimate and compare the incidence rates of selected clinical endpoints (listed as secondary endpoints in section “2.2 Endpoints”) among women receiving bazedoxifene and women receiving a bisphosphonate for treatment of osteoporosis.

To estimate and compare the incidence rates of selected clinical endpoints (listed as secondary endpoints in section “2.2 Endpoints”) among women receiving bazedoxifene and women receiving raloxifene for treatment of osteoporosis.

## **2.2. Endpoints**

The clinical endpoints for this study were determined based on the clinical and pre-clinical data from the bazedoxifene development program, class effects of other SERMs, and recommendations of the EU Rapporteurs.

Potential endpoints will be identified by an electronic search of the coded diagnosis fields of the medical records. The relevant diagnostic codes that will be used as operational definitions of each of the endpoints will be listed in the statistical analytic plan of the study. The available medical record of the identified cases for the primary endpoint will be retrieved and reviewed to confirm the diagnosis.

### **2.2.1. Primary endpoints:**

- Venous thromboembolism (VTE) defined as deep vein thrombosis (DVT), pulmonary embolism (PE), retinal vein thrombosis, and sinus thrombosis

### **2.2.2. Secondary endpoints:**

- Ischemic stroke
- Thrombotic and ischemic cardiac disorders (including myocardial infarction, myocardial ischemia, and coronary occlusion)
- Atrial fibrillation
- Biliary events: cholecystitis, cholelithiasis
- Hypertriglyceridemia

- Fractures
- Chronic and acute renal failure (including chronic renal insufficiency and end stage renal disease)
- Malignancies including breast, renal, ovarian, thyroid, gastrointestinal tract and lung cancers, as well as an aggregate of all malignancies
- Depression
- Selected ocular events including retinal vascular occlusions, disorders of the globe, iris, ciliary body, retina, eye adnexa and cornea.
- Goitre

### **3. STUDY DESIGN**

This post-authorization safety study (PASS) is an observational, non-interventional epidemiologic cohort study using data from a European database of electronic medical records.

#### **3.1. Data Source**

This study will use the Cegedim Longitudinal Patient Database (LPD), an electronic medical records database that collects clinical data from primary care physician practices in the following European countries i.e., Spain, Italy, Germany, France, Belgium and UK. (In the UK the database is known as The Health Improvement Network (THIN).) For this study the Cegedim LPD in Italy and Spain will be used. If during the recruitment period of the study bazedoxifene is launched in other European countries where Cegedim LPD is available, the study may be expanded to include those countries.

The Cegedim LPD obtains medical information from a proprietary practice management software used during physician office visits to capture clinical data in an electronic medical record system. Physicians use the practice management software developed by Cegedim to maintain electronic medical records of their patients. In each country a panel of physicians using this electronic system volunteered to make available anonymized patient-level information from their practices for clinical research purposes. Since these data are being collected in usual clinical care in a non-interventional way, they reflect routine clinical practice in these countries. The panel of contributing physicians is maintained as a representative sample of the primary care physician population in each country according to age, sex, and geographical distribution. Additionally in most countries, the patient population is representative of the respective country population according to age and sex distribution, as provided by national statistic authorities.

**Table 1: Doctor and patient populations in the Cegedim LPD by country**

	France	UK	Italy	Germany	Spain
Number of physicians in the panel	1200	1200	700	550	300
Average number of patients who consulted GP at least once in a year	1,600,000	1,400,000	800,000	680,000	320,000

The patient data in the LPD form a nationally representative sample. Data have been collected in Italy since 2004 and in Spain since 2006, providing several years of medical history, including comorbidity and concomitant medication use information. Of the patients included in the Spanish and Italian LPD, there are currently approximately 68,000 women with drug-treated osteoporosis. Between 1 and 6% of these patients are taking raloxifene, depending on the region; most of the rest are prescribed a bisphosphonate (Cegedim, data on file).

### **3.2. Contents of the Cegedim LPD**

Data are entered regularly during usual patient care, submitted daily to the Cegedim coordinating center, cleaned and de-identified, and then made available for research.

Anonymized patient data collected from each GP practice includes:

- Demographic information (age, gender)
- Medical history (event dates, diagnoses, risk factors, referrals to specialists)
- Therapeutic history (date/length of prescription, molecule/product, dosage)
- Additional information (test results, immunizations, height, weight, blood pressure)

Patient data collected by Cegedim in each country participating in the LPD varies to some extent to accommodate local needs. However, all countries collect data on medical comorbidities and outcomes, prescriptions, demographics, and physician characteristics.

In the Cegedim electronic medical record system diagnosis of clinical events are recorded as diagnostic codes. These codes from the different participating countries will be harmonized based on prespecified algorithms developed prior to the analysis and listed in the statistical analytic plan.

**Table 2: Data coding conventions in the different countries**

	France	UK	Italy	Germany	Spain
Drug code dictionary	Claude Bernard	Multilex	Farmadati	Abdata	Vademecum
Therapy classification	European Pharmaceutical Marketing Research Association (EphMRA)	British National Formulary (BNF)	Anatomical Therapeutic Chemical (ATC)	ATC	ATC
Disease classification	Home grown thesaurus mapped to International Classification of Diseases-10 (ICD-10) and International Classification of Primary Care-2 (ICPC-2)	Read Codes	ICD-9	ICD-10	Code CIAP mapped to ICD-9

Cegedim LPD does not collect hospitalization data directly except in the UK THIN database. Information on hospitalizations is captured in the patient's general practice file during follow-up visits with the patient's general practice physician following discharge from the hospital. However, this information is not systematically collected and there is no established linkage between the medical records at the general practices and at the hospitals.

#### **4. STUDY POPULATION**

All women in the Cegedim database meeting the inclusion criteria will be included in the analysis without any sampling process.

##### **4.1. Inclusion Criteria**

Subjects must meet all of the following inclusion criteria to be eligible for inclusion into the study:

1. Female
2. At least one prescription for bazedoxifene, raloxifene, or any bisphosphonate during the study inclusion period (index prescription);
3. A recoded diagnosis code of osteoporosis on or within 60 days prior to the index prescription date;
4. Age  $\geq 45$  at the date of the index prescription; and
5. At least 6-months of follow-up data in the electronic medical record system prior to the date of the index prescription

#### **4.2. Subject Accrual Period**

The study will operationally launch after bazedoxifene becomes commercially available in the participating countries. However, the subject inclusion period in the database will begin at the time of the commercial launch of bazedoxifene in each country (e.g., September 2010 in Spain, April 2011 in Italy) and will continue for **three** (3) years from the start of the study.

### **5. STUDY TREATMENT AND DURATION**

This study involves retrospective analysis of prospectively collected data in an existing electronic database for the purpose of usual clinical care. It is expected that osteoporosis medications will be used on the basis of the approved SmPCs and will be adjusted solely according to medical and therapeutic necessity. As this is a non-interventional study there is no study mandated dosing regimen or visit schedule. Physicians will be prescribing the drugs according to the standard clinical practice in the participating countries. There is no study mandated duration of therapy.

### **6. STUDY PROCEDURES**

#### **6.1. Follow up time and drug exposure time**

##### **6.1.1. Follow up:**

Each woman will be followed for identification of the selected endpoints for a period of up to five years from the date of the index prescription record for bazedoxifene, raloxifene or a bisphosphonate. The follow up will continue even if the woman discontinues the index medication or switches to a different medication during the five year period.

The follow up duration of an individual woman may be shorter than the five year period if the woman transfers out of her GP office that wrote the index prescription, or if the database records the death of the woman. In these situations the data will be censored on the date of transfer or the date of death.

##### **6.1.2. Drug exposure:**

Exposure to the drugs under study will be ascertained by searching the prescription records for the relevant product codes. For each prescription the duration of exposure will be

estimated based on the dose and quantity of the prescribed medication. For each prescription, person-time exposed to the drug will begin to accrue from the date of the prescription. The follow up time will be categorized into:

- **Current exposure:** defined as the duration of the prescription
- **Recent exposure:** defined as the 60-day period following the end of the duration of prescription
- **Past exposure:** defined as any follow up time accrued after 60 days following the end of the duration of the prescription.

A sensitivity analysis will be conducted with a different definition of exposure categories (e.g., using a 90-day window to define recent exposure).

Given the discontinuous nature of osteoporosis medication use, it is likely that a large number of women in this study will accrue ‘current use’, ‘recent use’ and ‘past use’ exposure time to multiple osteoporosis drugs during the 5-year period of follow up.

Drug exposure will also be categorized with respect to the cumulative exposure to each drug (e.g., 0-days, 1-30-days, 31-90-days, 91-180-days, 181-365-days, >365-days) to evaluate whether or not the incidence (hazard) of a specific adverse event varies with increased duration of use.

## 6.2. Study Period

It is expected that this study will take at least **nine** (9) years to complete, with a **3** year subject accrual period, 5 years of follow-up per patient and 1 year for data cleaning, analysis and report generation. Depending on the rate of uptake of bazedoxifene in the participating countries the accrual period may need to be extended to ensure adequate sample size. The patient accrual data will be reviewed annually to determine whether the uptake is sufficient to complete the study in the proposed time period.

## 6.3. Endpoint identification

The relevant diagnostic codes for each of the endpoints will be specified in the statistical analytic plan. Endpoints will be identified based on an electronic search for the relevant diagnostic codes in the diagnosis fields of the medical records during the follow up period.

For the identified potential cases, the electronic medical record will be retrieved and reviewed by a clinical expert to confirm the diagnosis for the following endpoints:

The primary endpoint:

- a. Venous thromboembolism (VTE) defined as deep vein thrombosis (DVT), pulmonary embolism (PE), retinal vein thrombosis, and sinus thrombosis.

Secondary endpoints

- b. Ischemic stroke
- c. Thrombotic and ischemic cardiac disorders (including myocardial infarction, myocardial ischemia, and coronary occlusion; and includes both acute and chronic disorders).
- d. Malignancies: Breast, ovarian, renal, thyroid and endometrial.
- e. Any ocular event with a vascular etiology (possibly indicative of retinal vein thrombosis, e.g. retinal arterial thrombosis, retinal hemorrhage, visual field defects of vascular origin).

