### 7.1. Sample Size Calculation

There is no active de novo patient enrollment in this study and all women in the database who meet the inclusion criteria during the recruitment period will be included in the analysis. Therefore, the focus of the sample size calculation was to determine the precision of the estimated incidence rate ratios (IRR) that can potentially be achieved in the study depending on several different hypothetical scenarios of subject accrual. Depending on drug uptake in the participating countries, speed of accrual, event rates, and actual dropout rates, the precision of the estimated incidence rate ratio may change.

The estimates are based on the expected incidence rate of VTE as the primary endpoint. It is estimated that the incidence rate of VTE in women who are not treated with a SERM or HT is 1.74/1000 patient-years (PY), based on data from the placebo groups in bazedoxifene clinical trials. It is assumed that women treated with raloxifene would have a higher incidence of VTE, of 2.17/1000 PY, based on data from the Phase III pivotal trials of bazedoxifene. The rate of VTE observed in the raloxifene arm of the bazedoxifene pivotal trials is lower than the rate reported in the Multiple Outcomes of Raloxifene Evaluation (MORE) trial [1]. In the MORE trial, the incidence rate of VTE was 3.5/1000 patient-years in women randomized to raloxifene. Therefore, our calculations are likely to be substantially more conservative than estimates based on rates in the literature.

All estimates (Table 3, Table 4) were calculated with two-sided 95% confidence intervals. According to the study plan, there will be a 3-year accrual period and each woman will be followed for up to 5 years from enrollment. Since osteoporosis therapies are chronic therapies, it is likely that women will be exposed to the drugs for more than one year. A conservative annual loss to follow up rate of 15% was used in the estimation. Estimates were based on Wald 95% confidence intervals [2]

**Table 3: 95% Confidence Intervals (CI) for Incidence Rate Ratios (IRR) with different numbers of patients in the BZA arm and the primary comparator arm**

Bazedoxifene (n)	Bisphosphonate (n)	BZA:Bisphosphonate	Underlying Incidence Rate Ratio (IRR)		
			1	1.5	2
			95% CI of observed point estimate of IRR		
2150	8600	1:4	0.6, 1.7	1.0, 2.4	1.3, 3.0
2000	8000	1:4	0.6, 1.8	0.9, 2.4	1.3, 3.1
1750	10,500	1:6	0.6, 1.8	0.9, 2.5	1.3, 3.1
1500	12,000	1:8	0.5, 1.9	0.9, 2.5	1.3, 3.2

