## **9. ADVERSE EVENT REPORTING AND SERIOUS ADVERSE EVENT REPORTING**

This study uses de-identified patient-level electronic health related databases (e-HRD), in which it is generally not possible to link (i.e. identify a potential association between) a particular product and medical event for any individual. Furthermore, while the identifiable patient criterion may be met, the identifiable reporter criterion will not. Thus, the minimum criteria for reporting an adverse event (i.e., identifiable patient, identifiable reporter, a suspect product, and event) are not available and adverse events are not reportable as individual AE reports.

However, this study protocol requires review of the patient medical chart and/or a narrative field in the dataset. If the reviewer identifies a SAE with explicit attribution to any Pfizer drug via patient chart and/or narrative review (and with an identifiable reporter), these SAEs should be reported to Pfizer or its representative for submission to regulatory authorities.

A serious adverse event (SAE) is defined as any untoward medical occurrence that at any dose:

- results in death;
- is life-threatening (i.e., at immediate risk of death due to the event);
- requires inpatient hospitalization or prolongation of existing hospitalization;
- results in persistent or significant disability/incapacity; or
- is a congenital anomaly/birth defect.

Medical and scientific judgment is exercised in determining whether an event is an important medical event. An important medical event may not be immediately life-threatening and/or result in death or hospitalization. However, if it is determined that the event may jeopardize

the patient or may require intervention to present one of the other outcomes listed in the definition above, the important medical event should be reported as serious.

Examples of such events are intensive treatment in an emergency room or at home for allergic bronchospasm, blood dyscrasias or convulsions that do not result in hospitalization, or development of drug dependency or drug abuse.

If there is a written notation in the medical chart/narrative field indicating that a physician attributed a serious adverse event to a Pfizer drug, Pfizer or its representative will complete an SAE form within 24 hours and submit it to Pfizer Safety. Such information will not include any patient or physician identifying information such as name, address, or phone number.

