6 ENDPOINTS AND COVARIATES

The following Primary end points and Secondary end points will be identified with appropriate diagnosis codes. The detailed list of diagnosis codes in each country is available in a separate document.

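### No masking step is stated for the expert confirmation of VTE and other endpoints, so the verdict is open to knowledge of the drug, and the SAP does not say how the verdict is used

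*Protocol*

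**What the plan says.** Protocol 2.2 and 6.3 find potential cases by a search of diagnosis codes and then confirm some of them. For the primary endpoint, 2.2 states: "The available medical record of the identified cases for the primary endpoint will be retrieved and reviewed to confirm the diagnosis". Section 6.3 extends this to ischemic stroke, thrombotic and ischemic cardiac disorders, five named malignancies and ocular events of vascular origin, for which "the electronic medical record will be retrieved and reviewed by a clinical expert to confirm the diagnosis".

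Protocol 3.2 lists what the database record holds, including "Therapeutic history (date/length of prescription, molecule/product, dosage".

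Protocol section 9 says that "this study protocol requires review of the patient medical chart and/or a narrative field in the dataset". It then adds a conditional duty: "If the reviewer identifies a SAE with explicit attribution to any Pfizer drug via patient chart and/or narrative review", and with an identifiable reporter, the event goes to the sponsor.

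Protocol 1.1 says of BZA that "VTEs are included in the product label as an important identified risk". Protocol section 10 concedes that hospital records are incomplete and that physicians cannot be queried about missing information. It does not list unmasked case review as a weakness.

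The SAP takes a different line. Its section 6 says: "The following Primary end points and Secondary end points will be identified with appropriate diagnosis codes". Section 8.1.1 relies on validated codes, and section 8.1.2 counts patients with a diagnosis. The SAP describes no case review.

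**The concern.** A confirmation step is a judgement. If the person judging can see which drug was prescribed, and already associates that drug with the event, the chance of confirming a borderline record may differ by cohort. That is differential outcome misclassification. It does not reliably pull the ratio towards 1. It can raise the BZA ratio, if a known risk makes the diagnosis look more plausible, or lower it, if the reader is sceptical.

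Three features leave room for this. VTE is a labelled risk of the study drug. The evidence is a GP record that may lack the hospital work-up. Neither document gives written criteria for confirmation or a second reader.

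The planned sensitivity analyses cover the exposure window, missing BMI, smoking and alcohol data, and the osteoporosis-diagnosis criterion. None concerns case confirmation, so such an effect would not show in the report.

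**Working it through.** **Step 1: is the drug visible to the person who confirms?**

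| Question | What the documents give |
|---|---|
| What is read? | The electronic (6.3) or available (2.2) medical record, with no stated restriction |
| Does it show the drug? | Yes: product, dosage and prescription dates (3.2) |
| Is anything removed first? | No step in either document |
| Does other text assume drug names are readable? | Yes: section 9, for explicit attributions |
| Is the section 9 reviewer the 6.3 expert? | Not stated; 2.2 and 6.3 describe the only chart review in the protocol |
| Does the SAP add a safeguard? | No: codes only, no review procedure |

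Unmasked review is therefore an inference from the record's content and the absence of a masking step. No sentence states it.

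**Step 2: how many events are at issue?** The plan gives no figure on this point, so this only sets the scale.

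Inputs from the documents: 1,823 BZA and 10,938 bisphosphonate women (SAP 5.4); a reference VTE rate of 1.74 per 1,000 PY (protocol 7.1); two-sided 95% Wald intervals.

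Mean follow-up is assumed. Compounding 15% annual loss over 5 years gives (1 − 0.85^5)/(−ln 0.85) = 3.42 years. Taking 5 × 0.85 gives 4.25 years, which reproduces 22 of the 24 limits in protocol Table 3, against 3 of 24 for 3.42. For example, for 1,750 against 10,500 women at IRR 1.5, 4.25 years gives 19.4 and 77.7 events and limits of 0.91 and 2.47. The table prints 0.9 and 2.5. Both follow-up values are carried forward.

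Expected events = n × years × 1.74/1,000 × IRR:

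| Mean follow-up | BZA, IRR 1 | BZA, IRR 1.5 | BZA, IRR 2 | Bisphosphonate |
|---|---|---|---|---|
| 3.42 years | 10.9 | 16.3 | 21.7 | 65.1 |
| 4.25 years | 13.5 | 20.2 | 27.0 | 80.9 |

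**Step 3: what do a few changed BZA verdicts do?** IRR = 6 × e1/e0, where e1 and e0 are the BZA and bisphosphonate counts. The limits are IRR × exp(±1.96 × √(1/e1 + 1/e0)).

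| True IRR | Follow-up | Change in BZA cases | Before | After |
|---|---|---|---|---|
| 1 | 3.42 | +3 | 1.00 (0.53–1.90) | 1.28 (0.71–2.28) |
| 1.5 | 3.42 | +2 | 1.50 (0.87–2.58) | 1.68 (1.00–2.83) |
| 1.5 | 4.25 | +2 | 1.50 (0.92–2.44) | 1.65 (1.03–2.64) |
| 2 | 3.42 | −3 | 2.00 (1.23–3.25) | 1.72 (1.03–2.88) |
| 2 | 3.42 | −4 | 2.00 (1.23–3.25) | 1.63 (0.97–2.76) |
| 2 | 4.25 | −5 | 2.00 (1.29–3.09) | 1.63 (1.02–2.61) |

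**Step 4: the same as confirmation proportions.** The documents give none, so these are assumed. Observed IRR = true IRR × (share confirmed in BZA / share confirmed in comparator).

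- 95% against 85% multiplies the IRR by 1.12. A true 1.5 is seen as 1.68, with limits 0.95–2.95 (3.42 years) or 1.01–2.78 (4.25 years).
- 90% against 70% multiplies it by 1.29. A true 1 is seen as 1.29, and the interval still includes 1.
- 70% against 90% multiplies it by 0.78. A true 2 is seen as 1.56, with limits 0.88–2.74 or 0.94–2.58.

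**The case against.** The strongest reply is that the SAP does not use the verdict. It identifies endpoints by code and counts patients with a diagnosis, so a biased reviewer might never touch the numerator. This stands in part. Bias in the analysed endpoint is not demonstrated, and amending 6.3 alone would not settle the matter. It does not remove the point: protocol section 7 sends major SAP modifications to a protocol amendment, so the SAP's silence does not cancel the confirmation that 2.2 and 6.3 require. The two documents leave the verdict's role open.

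A reader might infer from section 9 that the expert must look for events attributed to the sponsor's drug, and so reaches every verdict with the drug known. The text does not support that. The duty is conditional on explicit attribution and an identifiable reporter, and the same section says that the database does not generally meet the reporter criterion. It does not name the 6.3 expert. It is also compatible with masked review if the order of the two tasks is fixed. Section 9 shows only that nobody planned to hide drug names.

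A reader might also extend the labelled-risk argument to every reviewed endpoint. Protocol 1.1 names only VTE. Against raloxifene, any expectation would be partly shared, because protocol 7.1 assumes a raised VTE rate there too.

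**Conclusion.** The point holds as a gap in the plan that is cheap to close. As written, confirmation of VTE and four other endpoint groups is open to knowledge of the drug, no safeguard is stated, and the SAP does not say what the verdict does. The direction of any bias is unknown.

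The size depends on the true ratio. About 11 to 27 BZA VTEs are expected. Two extra confirmed cases bring the lower limit to 1 or just above it at a true IRR of 1.5, under either follow-up assumption. It would be tempting to say that two or three verdicts decide the study, but that fails at IRR 1 and at IRR 2. Hiding a true doubling takes about four rejected BZA cases at 3.42 years, and more than five at 4.25 years.

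These figures rest on the protocol's reference rate, the SAP's cohort sizes, the assumed follow-up and a crude Wald interval. They show what could happen if verdicts depended on the drug. They are not evidence that verdicts would.

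**What to change.** **Protocol 6.3.** Have the data holder supply an extract for each potential case, with names and codes of osteoporosis medicines removed from the prescription fields and, as far as possible, from free text. The reviewer records and locks the verdict on that extract.

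**Protocol section 9.** State that the unmasked record is opened for the SAE-attribution check only after the verdict is locked. The same reviewer can do both.

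**SAP section 6.** State that the locked verdict defines the confirmed endpoint. Report the proportion of potential cases confirmed in each cohort, and give the code-only result as a sensitivity analysis.

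**Cost.** Wording in three places, and redaction work. At 3.42 years, potential VTE cases in the BZA and sampled bisphosphonate cohorts number roughly 75 to 125. The low end is 10.9 + 65.1 = 76, with all confirmed at IRR 1. The high end is (21.7 + 65.1)/0.70 = 124, with an assumed 70% confirmed at IRR 2. At 4.25 years the high end becomes (27.0 + 80.9)/0.70 = 154. Raloxifene cases and the other reviewed endpoints come on top and are not sized here. If review precedes the bisphosphonate subsampling, the load is much larger: 82,041 × 3.42 × 1.74/1,000 is about 488 bisphosphonate VTEs. Some drug mentions in free text will probably remain.
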